7.2 Study Procedures

Provide a step by step description of all research procedures being conducted (broken down by visit, if applicable) including such information as below (where and when applicable); describe the following:

- HOW: (e.g., data collection via interviews, focus groups, forms such as surveys and questionnaires, medical/school records, audio/video/digital recordings, photographs, EKG procedures, MRI, mobile devices such as electronic tablets/cell phones, observations, collection of specimens, experimental drug/device testing, manipulation of behavior/use of deception, computer games, etc.)
- WHERE: (e.g., classrooms, labs, internet/online, places of business, medical settings, public spaces, etc.)

1. Once determined that a potential participant is eligible, research staff will provide an overview of the study and informed consent will be obtained. Participants will be informed that they will participate in their regularly scheduled NFP program visits in their homes and these visits will include additional information related to infant soothing, feeding, sleeping, active play.
2. Participants will be sent a link to an electronic survey hosted in REDCap prior to their first NFP visit that includes the enhanced content ("Soothing Your Baby"). A paper copy will be available if unable to access REDCap. Participants will be informed that they can skip any questions that they are not comfortable answering. The approximate time to complete this survey packet is 15 minutes. The survey packet will include demographic questions (e.g., age, marital status, education) as well as questions about their infant's sleep, their infant's bedtime routine, and mothers' use of soothing techniques for their infant. Up to 3 reminders will be sent via email or text message. If participant doesn't complete the electronic survey, the final reminder will include a note that a paper packet and prepaid return envelope will be mailed to the address on file.

7.2.1 Visit 1 or Day 1 or Pre-test, etc.

Provide a description of what procedures will be performed on visit 1 or day 1 or pre-test in order of how these will be done. If your study only involves one session or visit, use this section only and indicate 7.2.2 as not applicable.

3. NFP nurses will deliver the first of four content areas - "*Soothing Your Baby*" (e.g., infant temperament, crying norms, soothing strategies that work for your baby, and goal setting) during their home visit when infants are age 2-5 weeks. This content along with a goal setting activity will be discussed during regularly scheduled NFP program visit in the participant's home and will last approximately 20 minutes.

7.2.2 Visit 2 or Day 2 or Post-test, etc. (If applicable)

Provide a description of what procedures will be performed on visit 2 or day 2 or post-test in order of how these will be done. If your study involves more than two sessions or visits replicate this section for each additional session or visit (e.g., 7.2.3, 7.2.4, etc.).

4. Visiting nurses will deliver the second of four content areas - "*Feeding Your Baby*" (e.g., developmentally appropriate infant feeding, feeding on demand/when showing hunger signs, stop feeding when showing fullness signs, avoiding controlling feeding practices, bottle feeding guidance, and goal setting) during their home visit when infants are age 6-10 weeks. This content along with a goal setting activity will be discussed during regularly scheduled NFP program visit in the participant's home and will last approximately 20 minutes.
5. Following "*Feeding Your Baby*", nurses will instruct parents on how to use the Owlet Dream Sock that the infant will wear on their foot for 2-weeks. This device will only be used on a subset of families (i.e., the first 10 families) that have access to reliable home Wi-Fi and a smartphone. Infants' sleep data from the Dream Sock will connect to a smartphone app.

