1.0 Objectives

1.1 Study Objectives

Describe the purpose, specific aims or objectives. State the hypotheses to be tested.

Aim 1: To add a cardiovascular health (CVH) module focused on a responsive parenting intervention to the existing perinatal home visitation program delivered by Nurse Family Partnership (NFP) visiting nurses in the Northern Appalachian region of Central Pennsylvania.

Aim 2: To train selected NFP visiting nurses on the CVH module and assess the acceptability of the module as well as the fidelity of delivery to postpartum women and their infants.

Aim 3: To assess the feasibility of using a commercially available actigraphy device to measure infants' sleep in a subset of postpartum women and their infant.

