3.1 Inclusion Criteria

Create a numbered list of the inclusion criteria that define who will be included in your final study sample (e.g., age, gender, condition, etc.)

Inclusion criteria for this study area are as follows:

1. Mother-infant dyad enrolled in and receiving the NFP program through Geisinger Clinic or UPMC Home Health Care of Central PA
2. Mother age \geq 18 years at time of delivery
3. Mother English speaking
4. Singleton infant born at \geq 35 weeks' gestation
5. Infant age $<$ 1 month at time of consent
6. Reliable access to the internet for consent and data collection purposes
7. Willingness to download and access an app on personal smartphone (subsample of 10 people)

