All NFP visiting nurses participating in this study will be trained in screening procedures. No Protected Health Information (PHI) will be collected during screening procedures. Potential participants will be approached by NFP visiting nurses during late pregnancy (≥ 37 weeks' gestation) or following the birth of a live infant (within 1 month of delivery) at regularly scheduled home visits. However, enrollment for this pilot study will not occur until after the birth of a live infant (within 1 month of delivery). NFP visiting nurses will provide recruitment materials that include information about the study with potential participants and verbal consent will be obtained before any screening questions are asked of participants. Once a potential participant is deemed eligible after screening and expresses interest in participating, written informed consent will be obtained. Information collected as part of screening procedures will only be used to assess eligibility and will not be used in research analyses.

****Site Congruency: Is the information provided in the above section (Recruitment Methods) consistent across all relying sites in this research?**

Yes

No - Identify the sites that have dissimilar procedures: *[This field should solely identify the site.*

Dissimilar procedures across sites should be identified in the SITE workspace via HRP-XXX – R2S Site Plan]

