6.2 Waiver or Alteration of Authorization for the Uses and Disclosures of PHI

6.2.1 Access, use or disclosure of PHI representing no more than a minimal risk to the privacy of the individual.

6.2.1.1 Plan to protect PHI from improper use or disclosure.

Include the following statement as written – DO NOT ALTER OR DELETE unless this section is not applicable because the research does not involve a waiver of authorization. **If the section is not applicable, remove the statement and indicate as not applicable.**

Information is included in the “Confidentiality, Privacy and Data Management” section of this protocol or in “HRP-598 – Research Data Plan Review Form”.

6.2.1.2 Plan to destroy identifiers or a justification for retaining identifiers.

Describe the plan to destroy the identifiers at the earliest opportunity consistent with the conduct of the research. Include when and how identifiers will be destroyed. If identifiers will be retained, provide the legal, health or research justification for retaining the identifiers.

Authorization for Collection of Health Information: Authorization for the Owlet Dream Sock (infant sleep/actigraphy) will be obtained and documented during consent procedures. After consent is obtained, NPF visiting nurses will provide mothers with information on how to use the Owlet Dream Sock. Infants' sleep data from the Owlet Dream Sock will connect to a smartphone app on the mothers' phone. Nurses will discuss infants' sleep/actigraphy data (sleep quality, duration) with mothers during home visits. Infant sleep/actigraphy data will not be connected to identifying information.

6.2.2 Explanation for why the research could not practicably be conducted without access to and use of PHI.

Provide an explanation for why the research could not practicably be conducted without access to and use of PHI.

Authorization for Collection of Health Information: Authorization for the Owlet Dream Sock (infant sleep/actigraphy) will be obtained and documented during consent procedures. Given the that a primary goal of this pilot is to test the feasibility of using a commercial device to collect infant sleep/actigraphy data in a subset of study participants (n=10), study goals could not be met.

6.2.3 Explanation for why the research could not practically be conducted without the waiver or alteration of authorization.

Provide an explanation for why the research could not practically be conducted without the waiver or alteration of authorization.

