8.0 Number of Subject and Statistical Plan

8.1 Number of Subjects

Indicate the maximum number of subjects to be accrued/enrolled. Distinguish between the number of subjects who are expected to be enrolled and screened, and the number of subjects needed to complete the research procedures if applicable (i.e., numbers of subjects excluding screen failures.)

We anticipate enrolling 20 mother-infant dyads for this pilot study.

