8.2 Sample size determination

If applicable, provide a justification of the sample size outlined in section 8.1 to include reflections on, or calculations of, the power of the study.

Because this is a pilot study, no formal sample size calculations were completed.

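### The sleep sock goes only to equipped, app-willing families and those passed over are not counted, so lack of equipment and early refusal fall outside the planned Aim 3 feasibility result

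*Combined protocol and SAP*

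**What the plan says.** Aim 3 (section 1.1) is "To assess the feasibility of using a commercially available actigraphy device to measure infants' sleep in a subset of postpartum women and their infant". Sections 6.2.2 and 6.2.3 describe this as a primary goal of the pilot and fix its size: "collect infant sleep/actigraphy data in a subset of study participants (n=10". The whole study is small: "We anticipate enrolling 20 mother-infant dyads for this pilot study" (section 8.1).

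Entry to the sock subset is described in two places:

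- Section 7.2.2, step 5, places the sock after the feeding module, at infant age 6-10 weeks, with "a subset of families (i.e., the first 10 families) that have access to reliable home Wi-Fi and a smartphone". Willingness is not mentioned.
- Section 3.1, criterion 7, in the numbered entry list, reads "Willingness to download and access an app on personal smartphone (subsample of 10 people". Home Wi-Fi is not mentioned. Criterion 6, which applies to every dyad, is "Reliable access to the internet for consent and data collection purposes".

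Section 4.2.4 says of screening: "Information collected as part of screening procedures will only be used to assess eligibility and will not be used in research analyses". Section 6.2.1.2 adds that authorization for the sock is obtained and documented during consent.

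Section 8.3 plans descriptive feasibility statistics and gives recruitment, retention, fidelity and data collection methods as examples. It names no sock uptake measure and no denominator for one. No section asks for a record of families that lacked Wi-Fi or a smartphone, or that declined the app.

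**The concern.** The pilot prepares for a larger trial in a population that section 2.3 describes as lower income. There, owning the equipment and accepting the app are a large part of whether a commercial sock is feasible. Making both a condition of entering the Aim 3 sample means the result cannot reflect either, unless those passed over are counted. As written, they are not.

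The two entry rules also differ in timing and content. Criterion 7 stands among conditions settled at screening, before the infant is one month old. Step 5 applies weeks later and tests equipment. A mother who reaches the internet through mobile data could meet criteria 6 and 7 and still fail step 5. If a refusal of the app is recorded only as a screening answer, section 4.2.4 keeps it out of the analysis.

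At stake is the figure carried into the larger trial. A planner could take good wear and data capture among 10 pre-qualified families as a statement about the whole caseload, and under-provide for families who cannot or will not use the device.

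**Working it through.** **No plan figure to reproduce.** Section 8.2 states "Because this is a pilot study, no formal sample size calculations were completed", and no uptake rate, target or precision is given for the sock. The check therefore asks what 10 filled places would say about uptake.

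**Inputs from the documents.** Socks placed x = 10 (sections 3.1, 6.2.2 and 7.2.2). Dyads enrolled = 20 (section 8.1). Section 3.3.2 allows further recruitment after withdrawals, so 20 is not a firm ceiling on the number considered.

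**Step 1: uptake as a function of the number considered.** Uptake = 10/n, where n is the number of families considered until 10 socks are placed. The exact (Clopper-Pearson) 95% limits are: lower = the 2.5% point of Beta(10, n - 9); upper = the 97.5% point of Beta(11, n - 10), or 1 when n = 10. For n = 10 the lower limit is 0.025^(1/10) = 0.692.

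| Considered | Uptake | Exact 95% interval |
|---|---|---|
| 10 | 100% | 69.2-100% |
| 12 | 83% | 51.6-97.9% |
| 15 | 67% | 38.4-88.2% |
| 20 | 50% | 27.2-72.8% |

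With the subset as the only denominator, all four rows contain the same 10 families. These limits treat n as fixed. If counting stops at the tenth sock, the lower limits are unchanged and the upper limit becomes the 97.5% point of Beta(10, n - 10). For n = 20 that is 71.1% instead of 72.8%, a difference of no practical weight.

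**Step 2: would full slots be reassuring?** Let p be the share of families that are equipped and willing. The documents give no value, so a range is assumed. The expected number considered is 10/p. The chance that 20 dyads supply at least 10 such families is P(X ≥ 10), with X binomial(20, p).

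| Assumed p | Expected number considered | Chance that 20 dyads supply 10 |
|---|---|---|
| 80% | 12.5 | 0.999 |
| 70% | 14.3 | 0.983 |
| 60% | 16.7 | 0.87 |
| 50% | 20 | 0.59 |

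Even if four families in ten could not or would not use the device, the 10 places would probably still be filled. A full subset is weak evidence of feasibility.

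**Step 3: what the planned data still show.** Non-wear, refusal after instruction, app failure and lost data can be seen among the 10. Lack of home Wi-Fi, lack of a suitable smartphone and refusal before allocation cannot be read from any planned item.

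**The case against.** The best defence is that the plan defines no uptake rate, so none is distorted. Whether the sock measures sleep in equipped families is a legitimate conditional question for a single-arm pilot, and the feasibility list in section 8.3 is open-ended enough to take in a sock count. That stands in part: the fault is a missing denominator, not a miscalculated rate. But nothing now requires the count, and the reasons cannot be reliably recovered later.

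A reader might infer more than the documents support:

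- *That 10 and 20 families considered would look identical.* They need not. Electronic consent is time-stamped (section 5.2.1), nurses report recruits to the study centre (section 17.4), and the study must know who received a sock. Enrolment order would roughly separate the extremes among enrolled dyads. It would not give reasons.
- *That a mother who refuses the app is shut out of the 20.* Criterion 7 is limited to the subsample and can be read as leaving her in the study without a sock. Section 6.2.1.2 also has sock authorization documented at consent.
- *That section 4.2.4 bars all such information.* It covers screening. The Wi-Fi and smartphone check in step 5 comes after consent and could be analysed.
- *That passed-over families are certainly replaced.* This is inferred from the fixed 10. Step 5 could also mean the first 10 enrolled, with socks only for those equipped. A count below 10 would then show the loss, but that sits badly with the 10 stated in sections 3.1 and 6.2.
- *That the socks will cluster in one agency.* Nothing describes staggered starts or caseload shares, so there is no basis for an agency quota.

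**Conclusion.** The point holds as a gap in what Aim 3 can show. On the natural reading, that 10 places are filled from equipped and willing families, lack of equipment and refusal before allocation are not part of the planned feasibility result. The same 10 socks are compatible with uptake of 100% (69-100%) or 50% (27-73%), and lower still if more than 20 families are considered. These values are arithmetic on 10/n, not estimates: the documents contain no ownership or refusal rate.

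The conclusion rests on two things: that 10 is a number to be filled, and that no record of passed-over families is planned elsewhere. It does not extend to wear and data capture among the 10, which remain observable and valid for families of that kind. Criterion 7 and step 5 need aligning on either reading. This is an inexpensive improvement that should be made before recruitment, not a flaw that invalidates the pilot.

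**What to change.** 1. Take criterion 7 out of the general entry list in section 3.1. State it with the Wi-Fi and smartphone conditions in section 7.2.2 as one sock-subset rule, assessed after consent, so that the restriction on screening information does not apply.
2. At the feeding-module visit, take consented dyads in enrolment order until 10 socks are placed. Code each as placed, no home Wi-Fi, no suitable smartphone, app or sock declined, or other. A mother who joins the study but withholds sock authorization at consent counts as declined.
3. In section 8.3, report placed divided by considered with an exact 95% interval and the reasons. Report wear and data capture among those placed separately. If fewer than 10 socks are placed by the end of accrual, report the ratio reached.
4. State that the Aim 3 conclusion on wear and data capture applies to equipped, willing families.

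The cost is one coded field on the visit form and wording changes in sections 3.1, 7.2.2 and 8.3, with no extra participants, devices or visits. The downside is that reported uptake may fall below 100%.

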7.2.3 Visit 3 or Day 3 or Post-test, etc. (if applicable)

6. Visiting nurses will deliver the third of four content areas - "*Your Baby's Sleep*" (e.g., bedtime routines for adequate sleep, responding consistently to night waking, and goal setting) during their home visit when infants are age 10-16 weeks. This content along with a goal setting activity will be delivered during regularly scheduled NFP program visit in the participant's home and will last approximately 20 minutes.

6.2.4 Visit 4 or Day 4 or Post-test, etc. (if applicable)

7. Visiting nurses will deliver the fourth of four content areas - "*Playtime with Your Baby*" (e.g., tummy time, turning off devices during playtime, and goal setting) during their home visit when infants are age 16-20 weeks. This content along with a goal setting activity will be discussed during regularly scheduled NFP program visit in the participant's home and will last approximately 20 minutes.
8. Participants will be sent a link to an electronic survey hosted in REDCap after their last NFP visit that includes the enhanced content ("*Playtime with Your Baby*"). A paper copy will be available if unable to access REDCap. Participants will be informed that they can skip any questions that they are not comfortable answering. The approximate time to complete this survey packet is 15 minutes. The survey packet will include demographic questions (e.g., age, marital status, education) as well as questions about their infant's sleep, their infant's bedtime routine, and mothers' use of soothing techniques for their infant. Up to 3 reminders will be sent via email or text message. If participant

doesn't complete the electronic survey, the final reminder will include a note that a paper packet and prepaid return envelope will be mailed to the address on file.

7.3 Duration of Participation

Describe how long subjects will be involved in this research study. Include the number of sessions and the duration of each session - consider the total number of minutes, hours, days, months, years, etc.

Intervention content will be delivered by trained visiting nurses starting at the earliest postpartum home visit, which will occur within the first month after delivery, and conclude after the six-month postpartum home visit.

Four enhanced NFP program visits: approximately 20 minutes/visit, total time 80 minutes
Two survey packets: 15-20 minutes/packet, total time 30 minutes

Total time: approximately 1 hours and 50 minutes

7.4 Test Article(s) (Study Drug(s) and/or Study Device(s))

7.4.1 Description

Provide a brief description of all test articles (drugs (including any foods and dietary supplements), devices and/or biologics used in the research including the purpose of their use and their approval status with the Food and Drug Administration (FDA). Include information about the form of the drug product (e.g., tablets, capsules, liquid).

N/A

7.4.2 Treatment Regimen

Describe dose, route of administration and treatment duration. Include information about dose adjustments.

N/A

7.4.3 Method for Assigning Subject to Treatment Groups

Describe the randomization process and how the associated treatment assignment will be made.

7.4.4 Subject Compliance Monitoring

Insert the procedures for monitoring subject compliance.

N/A

7.4.5 Blinding of the Test Article

Describe how the test article is blinded.

N/A

7.4.6 Receiving, Storage, Dispensing and Return

7.4.6.1

Receipt of Test Article

Describe how the test article will be obtained and from what source. Describe how the study test article will be packaged along with amounts (e.g., number of tablets/capsules or volume of liquid) and labeling. If drug kits are used, describe all the contents of the kit and associated labeling.

N/A

7.4.6.2

Storage

Describe the plans to store, handle the test article so they will be used only on subjects and only by authorized investigators. Describe storage temperature requirements and how temperature will be monitored and recorded.

N/A

7.4.6.3

Preparation and Dispensing

Describe how the test article will be assigned to each subject and dispensed. Describe the steps necessary to prepare the test article. Include where the test article preparation will be done and by whom. Fully describe how the study treatment is to be administered and by whom.

N/A

7.4.6.4

Return or Destruction of the Test Article

Describe the procedures for final reconciliation of the test article supply at the end of the study and whether the test article is to be shipped back to a source or destroyed on site.

N/A

7.4.6.5

Prior and Concomitant Therapy

Describe what prior and/or concomitant medical therapy will be collected. Describe which concomitant medicines/therapies are permitted during the study. Describe which concomitant medicines are not permitted during the study.

N/A

****Site Congruency: Is the information provided in the above section (Study Design and Procedures) consistent across all relying sites in this research?**

Yes

No - Identify the sites that have dissimilar procedures: *[This field should solely identify the site. Dissimilar procedures across sites should be identified in the SITE workspace via HRP-XXX – R2S Site Plan]*

